Intervention Procedures: After target enrollment (n=240) is reached, YMCSM Peers will begin the intervention by posting materials according to the timeline developed in the ongoing E-PrEP content project. We will hold weekly project meetings (on different days) with Peers assigned to both E-PrEP and BxNow to ensure appropriate implementation, and to discuss logistical, ethical, or other issues that arise. For participants in the BxNow control arm, Peers will post about general health topics unrelated to HIV or sexual health (e.g. fitness, nutrition, smoking). If a control participant posts a question about PrEP, Peers will refer the individual to the CDC PrEP information site or answer the question privately. Content for both arms will be posted over a 6 week period, and outcome data will be collected via online surveys at baseline, 6, and 12 weeks and after 36 weeks (Table 13). Participants will be given \$20, \$30, and \$40 and 20 online gift-cards or through a Clincard as incentives after completion of assessments at T1, T2, and T3, and T4 respectively.

Anticipated components of E-PrEP: Potential components are listed in Table 2. *However, the exact contents, formats, and mode and timing of delivery of E-PrEP will be informed by input from Peers.*¹²³ We have successfully used this approach in *theSEXword* pilot, with ongoing engagement by participants. We will develop all components for both E-PrEP and the control condition (BxNow), and will also create an intervention activity guide for all 6 weeks, but the exact timeline for intervention delivery will be determined based on findings from Aims 1 and 2. We will thus standardize E-PrEP in its mode of delivery, types of digital media and contents, message framing, and sequence of topics posted and discussed, but Peers will tailor the exact language of posts based on their communication style. Components will be interactive wherever possible; for example, to target a factor such as perceived low risk, participants might assess their risk in an interactive poll, see results in real-time, compare themselves to others, and be engaged by Peers in discussions about risk. To address barriers to access, we might develop a brief time-elapsd video showing where and how to register at a clinic to obtain PrEP. All materials, including assessments, will be smartphone friendly, as most participants use mobile devices.

Table 1. Intervention Timeline

Component	Week	-4	0	6	12	36+
Participant Recruitment						

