Baseline Survey T1						
Exposure to Intervention						
Assessment T2 (intervention end)						
Assesment T3 (Post-intervention)						
Assesment T4 (Follow-Up)						

Developing BxNow (control condition): BxNow will focus on general health topics unrelated to HIV or sexual health (i.e. fitness, nutrition, smoking), but will also include basic information on PrEP as well as referral resources. We will develop a 6-week timeline to match the E-PrEP timeline, and we will compile publicly available digital media addressing general health topics (e.g. from CDC LGBT website). As with E-PrEP, standardized BxNow content will be delivered by Peers, using their own language. Additionally, after trial end (12 weeks), BxNow participants will be exposed to all E-PrEP components.

Setup of intervention sites: We will provide customized training and setup to the project team (PI, RA, Peers), establish 'E-PrEP' and 'BxNow' (control) private virtual communities (e.g closed Facebook group, private Twitter feed, private Tumbler blog), and implement systems for recruitment, consent, and online data collection (e.g. # of sites joined by each participant, engagement indicators for each posted component and for each participant, and other process measures).

Risk: Possible risks faced by the participant include: confidentiality issues, inconvenience and discomfort associated with interviews, potential risk compensation if PrEP is adopted, and fear that refusal to participate will affect relationship with Peers. More detail information about the potential risk and precautions against those risks can be found in the attached Protection of Human Subjects document sections I.4 and I.5.

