Compensation: Participants will be given \$20, \$30, and \$40 and \$20 as incentives after completion of assessments at baseline (T1), 6 weeks (T2), and 12 weeks(T3), and post 36 weeks (T4) (respectively). The participants will be given the choice to receive their incentives either via e-codes, Amazon online-gift cards, or by receiving a Clincard.

Data Collection:

We will collect three general types of data: 1) online processes (e.g. referral source, # of platforms joined by each participant); 2) measures of engagement with intervention components (e.g. # of views, time spent online); and 3) measures of outcome and independent variables, collected through online surveys at the ~~four~~three time points (see Table 2). To help assess both degree of exposure to intervention components and possible contamination between the two conditions, the surveys at 6 weeks (T2), ~~and~~ 12 weeks (T3) will display random samples of study and non-study graphics and posts and ask participants if they recall seeing them, with E-PrEP materials embedded in the choices.^{106,119,141}

Table 2. Data Collection					
Measures	Week	0	6	12	36+
PrEP intention, use, knowledge, attitudes		x	x	x	x
Perceived PrEP attributes		x	x	x	
HIV testing, risk behaviors		x	x	x	
Peer affinity and network data		x	x	x	

Table 2. Data Collection					
Measures	Week	0	6	12	36+
PrEP intention, use, knowledge, attitudes		x	x	x	x
Perceived PrEP attributes		x	x	x	
HIV testing, risk behaviors		x	x	x	
Peer affinity and network data		x	x	x	
Sociodemographic Factors		x			
Sexual Orientation		x			
Healthcare access		x	x	x	
Substance use		x	x	x	
Perceived risk, stigma		x	x	x	
Social media engagement		x	x		
Intervention exposure			x	x	

Data Security:

In order to securing information over the Internet and social media, and protecting participant data, an electronic, password protected and encrypted system will be developed to store analyses, and social media activity will remain private to study participants.¹⁶⁴ Research participants will be informed of how communications are recorded and stored during the online informed consent process. Due to the ever-changing and evolving nature of privacy issues on social media sites, we will review privacy settings for all social media study sites at least every four weeks and adjustments will be made to the study sites as necessary.

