1. <https://www.qualtrics.com/support/survey-platform/survey-module/survey-options/survey-protection/#PreventingRespondentsFromTakingYourSurveyMoreThanOnce>

Furthermore, we will download the raw data and store it in a password protected *and* encrypted file on the office computer of [name]. Only the PIs and research study staff will have access to the full data-set.

Analytic Plan: Our *primary outcome* will be *intention to use PrEP*,⁸³ which we consider a predictor of subsequent use,¹⁴² and will be measured using a Likert scale. We will use ‘intention’ as a proxy given the low likelihood of actual PrEP use.^{83,132,143} *Secondary outcomes* will be PrEP use, knowledge,¹⁴³ perceptions about PrEP¹³⁴ and HIV testing- and risk-behaviors.¹⁴⁴ *Covariates*^{80,81,143,145-148} will include access to medical care (including HIV/STI testing), sexual orientation, HIV and PrEP related stigma, substance use, sociodemographic factors,¹⁴⁴ social media engagement and network data,^{149,169} and perceived affinity to the referring Peer.¹⁵⁰ First, we will compare groups for equivalence at baseline, using chi-square or t-tests as appropriate. In addition, we will determine whether subgroups (e.g., grouped by number of social media sites joined, social media platform(s) used, peer referent, race/ethnicity, and sexual orientation) differ with respect to the primary and secondary outcomes. Relevant differences will be used as covariates in subsequent models. At each time point, we will examine change in our primary outcome variable (*intention to use PrEP*) by using a traditional two-sample test of proportions. To compare differences in outcomes between arms over time, we will use

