repeated measures mixed-effects logistic and linear models, with the treatment arm as a fixed-effect, Peers as a random-effect, and time (as a linear term) as an independent variable. We will also look at residual plots to determine if we need to include non-linear terms for time. Next, we will use hierarchical models to examine the role of secondary outcomes as potential mediators of change over time, e.g. are there differences by condition in PrEP knowledge or perceptions that account for differences in intentions. Finally, we will assess the impact of the exposure arm (E-PrEP or BxNow) and selected covariates (significant in the bivariate analysis at $p < 0.1$) on the primary and secondary outcomes using mixed-effects models. We will also assess the impact of online process and engagement variables on outcomes. To overcome possible limitations due to intra-cluster correlations, we will include a modified sensitivity analysis that examines outcomes in relation to participants' network size and perceived affinity to the Peers. To test *feasibility*, we will assess online process measures, including participation rate (# of individuals screening eligible and then ultimately joining the study), engagement activity (e.g. time spent viewing posted videos, # of responses posted to questions, participation in polls, etc.), and retention (# of participants actively 'leaving' or 'un-joining' a social media study site and # of respondents to follow-up assessments).

Power Analysis: The primary purpose of this study is to test feasibility and to obtain an effect size estimate for a future R01 application. We estimate that a sample size of 220, accounting for up to 20% attrition¹⁰⁶ will provide 80% power to detect an effect size of 20% in E-PrEP vs. 5% in BxNow in the proportion of participants indicating '*intention to use PrEP*' at 6 weeks, with a two-sided $\alpha < .05$. We will also have adequate power to detect a smaller effect size at 12 weeks because of our repeated measures design. This conservative effect size estimate is reasonable, given the novelty of the proposed intervention, the absence of other studies assessing uptake of a biomedical tool in YMSM, and the results of other studies assessing potential interest in PrEP.⁸³

Procedures outlined below have been guided by [name] (Consultant), and by [name] (Consultant), who has extensive experience in conducting online survey and intervention studies with vulnerable populations including MSM.

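### The trial is sized for one 6-week comparison, but the Analytic Plan does not make that comparison primary among its per-visit tests and models

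*Combined protocol and SAP*

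**What the plan says.** The Analytic Plan names intention to use PrEP as the primary outcome, "and will be measured using a Likert scale". It continues: "At each time point, we will examine change in our primary outcome variable", "by using a traditional two-sample test of proportions". It does not say which two samples are meant. E-PrEP and BxNow are the natural reading, since a two-sample test would not suit change within a person.

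For differences between arms over time it then specifies "repeated measures mixed-effects logistic and linear models, with the treatment arm as a fixed-effect", Peers as a random effect and time entered linearly. Further mixed models with selected covariates follow. No visit is called primary, the per-visit tests and the models are not ranked against each other, and no multiplicity adjustment appears.

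The Power Analysis is more specific. The planned sample "will provide 80% power to detect an effect size of 20% in E-PrEP vs. 5% in BxNow", at 6 weeks and a two-sided 5% level. Its next sentence claims adequate power for a smaller effect at 12 weeks.

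The status of the last survey is unsettled. Intervention Procedures says "outcome data will be collected via online surveys at baseline, 6, and 12 weeks and after 36 weeks", and Table 2 under Data Collection marks intention at 36+ weeks. The text above that table reads "collected through online surveys at the ~~four~~three time points". Under Developing BxNow, "after trial end (12 weeks), BxNow participants will be exposed to all E-PrEP components".

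**The concern.** A sample-size assumption is not a decision rule. The plan was sized for one test at one visit, but it describes a test at each visit plus models over time, with nothing to say which result answers the efficacy question. An analyst following it would hold several unranked results on the primary outcome and could lead with any of them.

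Two things are at stake. One is the chance of a false signal of preliminary efficacy, which the Aims include. The other is the effect size for a future grant application, which the Power Analysis gives as part of the study's primary purpose. If the visit is chosen after the results are seen, that estimate tends to be too large.

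**Working it through.** **1. What the stated sample size assumes.** Inputs from the Power Analysis: 20% vs 5%, two-sided 0.05, 80% power, 20% attrition, total 220.

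Per arm, pooled normal approximation: n = [1.960 × √(2 × 0.125 × 0.875) + 0.842 × √(0.20 × 0.80 + 0.05 × 0.95)]² / 0.15² = (0.9167 + 0.3834)² / 0.0225 = 75.1.

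With continuity correction: (75.1 / 4) × [1 + √(1 + 4 / (75.1 × 0.15))]² = 87.95, so 88 per arm and 176 in total. Allowing for attrition: 176 / 0.80 = 220, an exact match.

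Other variants miss: 190 without continuity correction, about 183 unpooled, 175 by arcsine, and 150 or 180 one-sided (without or with correction). So 220 corresponds to one test at 6 weeks at the full 5%, with no allowance for several visits and no design effect.

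**2. Error rate if either 6 or 12 weeks could be claimed.** With two unadjusted tests at 5% and independent visits: 1 − 0.95² = 9.75%. For correlated visits, P(|Z₁| > 1.96 or |Z₂| > 1.96) was simulated with 2 million draws. The documents give no correlation, so these values are assumptions:

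| Between-visit correlation | Chance of at least one false positive |
|---|---|
| 0 | 9.75% |
| 0.3 | 9.5% |
| 0.5 | 9.1% |
| 0.7 | 8.4% |
| 0.9 | 7.1% |
| 1 | 5.0% |

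If only 6 weeks counts, the number of visits adds nothing and the nominal level is 5%.

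**3. Bias from choosing the larger visit effect.** With 88 analysed per arm, the standard error of the difference is √[(0.16 + 0.0475) / 88] = 0.0486, or 4.9 percentage points. If the true effect is the same at both visits, the larger of the two estimates exceeds it on average by SE × √[(1 − ρ) / π]:
- ρ = 0: 4.86 × 0.564 = 2.7 points
- ρ = 0.5: 4.86 × 0.399 = 1.9 points
- ρ = 0.9: 4.86 × 0.178 = 0.9 points

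These compare with a planned difference of 15 points.

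**4. What naming the visit does not cure.** The two-sample test ignores clustering by Peer. With 15 recruits per Peer less 20%, 12 are analysed per Peer. The design effect is 1 + 11 × ICC, and the true level of a nominal 5% test is 2 × [1 − Φ(1.96 / √design effect)]. For an assumed ICC of 0.01 the design effect is 1.11 and the level 6.3%. For 0.05 they are 1.55 and 11.5%.

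**5. Adjusting instead of ranking.** Bonferroni over 6 and 12 weeks (0.025 each), by the step 1 method, needs 105 per arm: 210 / 0.80 = 262.5, so 263. That exceeds the planned 240. Ranking the visits needs no added participants.

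**The case against.** The strongest reply is that the deciding visit can be found: the Power Analysis attaches both the alpha and the power to 6 weeks, and 220 reproduces exactly as that one test. This stands in part. A reader might infer that the protocol names no primary visit anywhere and so fails to deliver its 5% level. The documents do not support that. What is missing is the link from the power statement to the Analytic Plan.

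A reader might also infer that every test and model is run at 5% and that success may be declared at any visit. Neither is written. No level is given for the per-visit tests or the models, and no success rule is stated. The per-visit tests could even be read as description, with the mixed model carrying the arm comparison. But the model as written has time as a linear term and specifies no week-6 contrast, so that reading does not deliver the comparison the trial was sized for.

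Third, it is tempting to count 36+ weeks as another efficacy test, which would raise the figure to about 11 to 14% at assumed correlations of 0.7 to 0.3. This is not secure. Section I.2 takes effectiveness measures from 0, 6 and 12 weeks, the Section I.1 table lists surveys at those same weeks, Developing BxNow puts trial end at 12 weeks, and Section I.6 places the controls' final survey there. Collecting intention later is not the same as planning a test of it.

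Finally, this is mainly a feasibility study. That limits the severity. It does not remove the point, because an unbiased effect size estimate is part of its stated purpose.

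**Conclusion.** The point holds in a limited form. The Analytic Plan's each-visit rule does not match the single 6-week test for which the trial was sized, and neither the visits nor the analyses are ranked.

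If significance at either 6 or 12 weeks were taken as a signal, the false-positive chance would be about 7 to 10%, and reporting the larger effect would overstate it by roughly 1 to 3 points on average. Both figures are conditional on the result being used that way, which the documents neither state nor exclude. They rest on assumed correlations between 0.9 and 0 and on no clustering; the bias figure also assumes equal true effects at the two visits. A 36+ week arm comparison is not clean in any case, because controls have by then been given the E-PrEP content.

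The change should be made, because it is cheap and protects the estimate the study is meant to provide.

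**What to change.** State in the Analytic Plan that the single primary comparison is E-PrEP vs BxNow in the proportion intending to use PrEP at 6 weeks (T2). Estimate it as the week-6 arm contrast from the mixed-effects logistic model, with Peer as a random effect and visit as a categorical term with an arm-by-visit interaction. This replaces the unclustered two-sample test. Label 12 weeks secondary and 36+ weeks descriptive.

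The cost is a few sentences. Naming the visit leaves N unchanged. Both parts are needed: the visit settles which result counts, and the clustering-adjusted model addresses the level at which it is tested. Whether the sample is large enough once clustering is allowed for is a separate question, since 220 contains no design effect. The small downside is that a significant 12-week result alone could no longer be presented as the primary finding.

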Rather than an alternative medium for implementation of existing interventions designed for in-person contact, social media may be a true 'game changer'^{74,76,77,121,122} to engage hard to reach individuals. While many online behavioral interventions exist, including some that use social media,¹⁶⁹ ours will be the first to use social media to facilitate uptake of a biomedical intervention. E-PrEP will connect the target population (YMCSM) to a new prevention tool (PrEP) through rapid linkage to medical care, accelerating diffusion of PrEP. Given the paucity of data regarding social media-based interventions to change health-related behavior, E-PrEP may have a marked impact on future bio-behavioral interventions, especially those that include diffusion of innovation.

Social media offers the power of scale and efficiency for large potential impact, even with relatively low intensity interventions.^{77,109,122} Similarly, PrEP, if widely adopted in high-risk populations and offered with behavioral interventions, could markedly decrease HIV infection rates. Social media-based, peer-led approaches like E-PrEP could be used to enhance efforts by community based and other organizations that employ internet-assisted or peer-outreach strategies to improve health.⁷⁶

Aims: To test the feasibility and preliminary efficacy of E-PrEP for increasing PrEP adoption in a cluster-randomized controlled trial.

Methods

Participants: The 16-20 peers will be randomized 1:1 to either E-PrEP or BxNow (control condition). They will then recruit n=240 total participants (120 for E-PrEP and 120 to BxNow). Each Peer will recruit approximately n=15 participants.

Inclusion criteria: Male or trans individuals; Ages 18-29; Have had unprotected anal sex with a male partner in the prior 12 months; Fluent in English or Spanish; Are HIV negative or unknown status (self-report); Identify as Black and/or Latino

Exclusion criteria: YMCSM or trans individuals who do not consent/assent to study; Are currently taking PrEP for HIV prevention, not currently using at least one of 3 social media sites that will be used for the E-PrEP intervention (e.g. not using Facebook, Twitter, Tumblr).

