Compensation for Peer Leader participants. Peers will be compensated for their time and travel and incentivized to actively participate in each visit by providing a ClinCard up to a total of \$425 over the course of the study for 9 visits. Peer Leaders will receive the incentive by having it added to a debit card, after attending each visit. The payments will occur as follows: Visit 1: \$30, Visit 2: \$40, Visits 3-4: \$45 each, Visits 5-7: \$50 each, Visit 8: \$55, Visit 9: \$60. Peers will not receive any compensation for visits in which they do not attend. Additionally, Peer Leaders may be able to receive an additional \$60 for each of two optional follow-up visits after the completion of intervention (up to two more visits).

Training in Ethical Conduct of Research for Peer Leaders: Although we will be collecting data from the Peers in order to evaluate the study and the Peers are also research subjects in this study, as part of the overall intervention, Peers will be conducting online recruitment and outreach and therefore we will make sure that Peers have a clear understanding of their roles in this capacity. We will initially conduct a two-session training with the Peers where they will go through our community research ethics training. I adapted this training from a World Health Organization training manual for lay community members, such as our Peers, participating as 'community researchers' to make accessible to them training in research ethics. It covers topics in history of research ethics, privacy and confidentiality, vulnerable subjects, ethical recruitment practices, protecting against risks, minimizing risks, and personal safety and conduct. This training has previously used with community partners for whom the CITI course is inaccessible due to literacy and/or language barriers. Additionally, we will have ongoing trainings throughout the project period in online privacy, security issues, and confidentiality with information. Peers in the study are not key personal, however we believe it is important that they do understand research ethics.

PROCEDURES FOR GENERAL PARTICIPANTS

Recruitment:

1. We will first randomize the 16 to 20 peers, 1:1 to either E-PrEP or BxNow (control condition).
2. Peers will then recruit n=240 participants total from their personal online social networks to their assigned condition (E-PrEP or BxNow). On average, each peer will recruit approximately 15 participants each.

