I.1 HUMAN SUBJECTS INVOLVEMENT AND CHARACTERISTICS: In table 1 below, we summarize the project’s activities, the number of participants who we project will participate in each activity, and the amount of reimbursement each participant will receive for these activities.

Table 1. Summary of project activities and compensation		
Activities	Participants	Compensation per participant
To pilot test E-PrEP and determine preliminary efficacy		
120 online surveys in control group at each time point (0, 6, 12 weeks)	120 YMCSM participants	(online gift-cards or via a Clincard) \$20/\$30/\$40/ \$20 assessment
120 online surveys in experimental group at each time point (0, 6, 12 weeks)	120 YMCSM Participants	\$20/ \$30 / \$40 / \$20 assessment
Total	240 unique individuals	---

I.1.2. Participants: The 16 peers will be randomized 1:1 to either E-PrEP or BxNow (control condition). They will then recruit n=240 total participants (120 for E-PrEP and 120 to BxNow). Each Peer will recruit approximately n=15 participants. In an effort to support recruitment efforts, members of the research team will buy Facebook ads to outreach to potential participants. We will assign participants randomly with equal number to each of the peer members who are having trouble with recruitment.

Inclusion criteria: Male; Ages 18-29; Have had unprotected anal sex with a male partner in the prior 12 months; Fluent in English or Spanish; Are HIV negative or unknown status (self-report); Identify as Black and/or Latino

Exclusion criteria: YMCSM who do not consent/assent to study; Are currently taking PrEP for HIV prevention, not currently using at least one of 3 social media sites that will be used for the E-PrEP intervention (e.g. not using Facebook, Twitter, Tumblr).

Recruitment:

1. We will first randomize the 16 peers, 1:1 to either E-PrEP or BxNow (control condition).
2. Peers will then recruit n=240 participants total from their personal online social networks to their assigned condition (E-PrEP or BxNow). On average, each peer will recruit approximately 15 participants each.
3. Peers will actively recruit online within their pre-existing social networks using text messages, brief videos, and picture graphics, using whichever mode is deemed appropriate. These recruitment advertisements will be co-developed by the Peers and investigators. Peers will then post the designated messages to their online social networks.

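### The arm comparison in the mixed models rests on 16-20 randomised Peers and the plan names no small-sample method; large-sample inference would give a 5% test of a score outcome a true size of about 6-9% at a plausible (assumed) intra-Peer correlation.

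*Combined protocol and SAP*

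**What the plan says.** The unit of randomisation is the Peer. Methods, Participants: "The 16-20 peers will be randomized 1:1 to either E-PrEP or BxNow (control condition". Recruitment item 1 under Procedures for General Participants gives the same range ("We will first randomize the 16 to 20 peers, 1:1 to either E-PrEP or BxNow (control condition"), while section I.1.2 gives a single number ("We will first randomize the 16 peers, 1:1 to either E-PrEP or BxNow (control condition"). On cluster size: "They will then recruit n=240 total participants (120 for E-PrEP and 120 to BxNow", and "Each Peer will recruit approximately n=15 participants".

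The Analytic Plan assigns the comparison of arms over time to "repeated measures mixed-effects logistic and linear models, with the treatment arm as a fixed-effect, Peers as a random-effect", with a linear time term. It does not say how the arm effect will be tested: no ML or REML, no degrees of freedom, no permutation or Peer-level test. One further step is aimed at intra-cluster correlation, a sensitivity analysis on network size and affinity to the Peer. It examines possible explanatory variables and does not supply a correction for few clusters.

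The two-sided 5% level ("with a two-sided $\alpha < .05") appears once, in the Power Analysis, for the proportion intending to use PrEP at 6 weeks. For that outcome the Analytic Plan also names, at each time point, an ordinary two-group comparison of proportions that takes no account of Peer.

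**The concern.** Putting Peer in the model as a random effect is the right step for a trial that randomises Peers, but it does not finish the job. The arm effect is a contrast between 8-10 Peers and 8-10 others. Its standard error depends on a between-Peer variance estimated from 14-18 degrees of freedom, and that estimate can fall to zero. A z or likelihood-ratio test treats the variance as known. With so few Peers, p-values come out too small and intervals too narrow whenever between-Peer variation matters.

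At stake are the preliminary-efficacy claim and the interval around the effect estimate that is meant to inform a later grant application. Because the method is left open, the result could also depend on a software default, or on a choice made after the data are seen.

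**Working it through.** **Inputs from the documents.** Peers K = 16 to 20. Participants 240, or the 220 of the Power Analysis; up to 20% attrition. Rates 20% against 5%; 80% power; two-sided 5%.
- From 240: 240 × 0.8 = 192 analysed, so 12 per Peer (K = 16) or about 10 (K = 20).
- From 220: 220 × 0.8 = 176 analysed, so 11 or about 9 per Peer.

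**Assumed, because the documents give no figure.** ICC 0 to 0.20; equal cluster sizes; within-participant correlation 0.5 (linear) or 0.4 (logistic).

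**1. The plan's own figure.** The plan says that 220 "will provide 80% power to detect an effect size of 20% in E-PrEP vs. 5% in BxNow". The usual two-proportion formula gives 76 per arm, or 88 per arm with continuity correction. Then 2 × 88 = 176, and 176 / 0.8 = 220, an exact match. The 220 therefore treats participants as independent.

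**2. Limiting size for a linear model.** When between-Peer variance dominates, the REML statistic follows t on K − 2 degrees of freedom. ML shrinks the variance by (K − 2)/K, so the cut-off of 1.96 acts as 1.96 × √((K − 2)/K).

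| | K = 16 (14 df) | K = 20 (18 df) |
|---|---|---|
| REML: P(\|t\| > 1.96) | 7.0% | 6.6% |
| ML: effective cut-off | 1.833 | 1.859 |
| ML: true size | 8.8% | 7.9% |
| Correct 5% cut-off | 2.145 | 2.101 |
| Correct / 1.96 | 1.094 | 1.072 |

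The last row is the source of the 7-9% for interval width.

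**3. Simulated size with no arm effect, linear models, cut-off 1.96.**

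| Setting | REML | ML |
|---|---|---|
| One time point, 16 Peers × 11, ICC 0.05-0.20 | 6.4-7.0% | 7.6-8.8% |
| One time point, 20 Peers × 9, ICC 0.05-0.20 | 6.0-6.7% | 6.9-8.0% |
| Three time points, Peer-only random effect | 6.4-7.1% | 7.6-8.9% |
| One time point, ICC 0 | from 4.1% | from 4.6% |

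At ICC 0.02 with one time point the range is 5.1-6.0%.

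**4. Simulated size, logistic models, Wald z.**
- One time point, ICC 0-0.20: about 1.7-3.2% at a 5% rate, 3.9-7.3% at 20%, 4.4-8.3% at 40%.
- Three time points, Peer-only random effect, ICC 0.01-0.10: 5.2-8.7% at a 5% rate, 7.1-8.8% at 20%.

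The low value at a 5% rate comes from sparse events: 96 per arm × 0.05 is about 5 events. A t reference there lowers the size from about 2% to about 1%, so the missing correction is not its cause.

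**5. Does Peer-based inference restore the level?**
- Linear REML with t on K − 2: about 4.4-5.0% at one time point with ICC 0.05 or more (down to 2.6% at lower ICC), and 4.7-5.2% with three time points.
- Linear ML with the same t reference still reaches 6.5% with 16 Peers, so REML is needed too.
- A t-test on Peer-level proportions: 3.5-5.8% across the binary settings tried, and 3.9-5.4% in a second set of 40,000 null trials per setting (rates 5%, 20% and 40%).

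**6. For comparison, the test of proportions that ignores Peer.** With 12 per Peer its size is 2Φ(−1.96/√(1 + 11 × ICC)): 6.3% at ICC 0.01, 11.5% at 0.05 and 17.6% at 0.10.

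**The case against.** A reader might infer that the trial's stated 5% level is not delivered and runs from about 2% to 9%. The documents do not support that, for four reasons.

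- The plan is silent on estimator and reference distribution. It does not commit to uncorrected inference, and an analyst who used REML with Kenward-Roger would be within its wording.
- The range is not a property of the plan. The top needs ML; with REML, linear models stop at about 7%. All the figures depend on an ICC that the documents do not give.
- The bottom belongs to a single-time-point logistic model at a 5% rate and is caused by sparse events. With three time points and a Peer-only random effect, the same rate gives about 5-9%.
- The 5% level is stated for the 6-week proportion, not for the mixed models. For that proportion, the test that ignores Peer is the larger threat (step 6) and a separate matter.

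Two further points stand. Degrees of freedom alter p-values and intervals, not the point estimate, so the effect estimate itself is not made optimistic. And the main purpose is feasibility and effect estimation, which limits the harm. The plan also specifies no arm-by-time term. If one were tested, its size would depend mainly on the random-effect structure (below 1% to above 10% in rough calculations), not on the number of Peers.

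None of this removes the gap. The design has few clusters, the inferential method is unstated, and the common large-sample choice errs in a known direction for score outcomes.

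**Conclusion.** The concern holds in conditional form. With 14-18 between-Peer degrees of freedom and large-sample inference, the arm-effect test on score outcomes has a true size of about 6-7% (REML) or 7-9% (ML), given an ICC of 0.05 or more, or repeated measures with a Peer-only random effect. At an ICC of 0.02 or less with one time point it is about 4-6%, which is of little consequence. For binary outcomes, expect about 5-9% with three time points and a Peer-only random effect. The figure of about 2% is confined to the sparse single-time-point Wald test. Intervals based on 1.96 are about 7-9% too narrow. The limiting values rest only on the number of Peers and the estimator; the rest depends on the assumed correlations and equal clusters. This should be fixed, but it does not threaten the feasibility aims.

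**What to change.** State in the Analytic Plan that every arm effect uses Peer-based inference:

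- **Linear models:** REML with Kenward-Roger degrees of freedom, or Peers minus 2.
- **Binary outcomes, including 6-week intention:** test the arm effect by a t-test on Peer-level proportions (14-18 df) or by a permutation test over the Peer allocation, and derive the 95% interval the same way. This also covers the outcome now assigned to a test that ignores Peer.
- **Mixed logistic model:** keep it for description over time and with covariates, since a Peer-level test uses neither the repeated measures nor the covariates.

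Also reconcile the number of Peers (16 or 16-20), because it sets the degrees of freedom.

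The cost is text, a little code and a change of primary test for binary outcomes; design and data collection do not change. Intervals widen by about 7-9%. Simulated power for 20% against 5% with 16 Peers × 11 analysed falls from 81% to 78% at a latent ICC of 0.05, and from 76% to 69% at 0.10. These power figures were not independently checked and are indicative only.
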